### **Nonstructural Valve Dysfunction and Structural Valve Deterioration**

The percentage of subjects experiencing nonstructural valve dysfunction and structural valve deterioration within the early post-operative period (within 30 days of implant) will be reported. Linearized rates will be used to summarize nonstructural valve dysfunction and structural valve deterioration for the late (>30 days) post-operative period. The linearized rates will be reported as the number of nonstructural valve dysfunctions and structural valve deteriorations occurring after the early post-operative period per year of subject exposure. The 30-day frequency and linearized rate for nonstructural deterioration and structural dysfunction will be stratified by the nature of the dysfunction.

## **11.4 EFFECTIVENESS ANALYSIS**

### **Subject functional classification**

Subjects will be stratified according to the NYHA classification preoperatively, at 6 months and annually post implant for 8 years. The distribution (numbers of subjects and percentages) in the various NYHA classes will be tabulated at each follow-up interval.

The primary effectiveness analysis will include all the subjects who survived the implant procedure and have at least one post-implant NYHA assessment. The proportion of the subjects in NYHA Classes I and II at 8 years post implant will be calculated to determine if it is  $\geq 75\%$  using a one-sided Binomial exact test. For subjects who die, withdraw or are lost to follow-up before reaching the 8 year follow-up visit, the last observed NYHA classes will be used in this analysis. As a consequence, those subjects will be counted as failures if they were in NYHA Classes III or IV at the time those events occurred. Subjects whose status at the time of the events is not known will be counted as failures if they were in NYHA Classes III or IV during their last assessment prior to the time of the events.

The proportion of subjects in NYHA Classes I and II and proportion of subjects who died and were in NYHA Classes III and IV at death or at their last known NYHA classification will also be calculated at each annual report.

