#### 4.2.3 PRIMARY EFFECTIVENESS ENDPOINTS

The primary effectiveness endpoint will be:

Proportion of subjects in NYHA Functional Classification I and II at 8 years post-implant.

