where  $p$  is the proportion of the subjects in NYHA Class I or Class II at 8 years post implant. The expected proportion of the alive subjects in NYHA class I or II at eight years is above 90%, based on 8 year follow up data for the Carpentier-Edwards PERIMOUNT 2700/2800/2900 valve (this proportion is above 90% within the subjects with valid NYHA assessment at each annual visit till 8 years follow up). Based on this expected proportion, a sample size of 45 subjects provides 85% power to test the hypothesis that the true proportion is greater than 75% using an exact binomial test. Thus, the sample size of 101 subjects with NYHA data at 8 year post implant is more than adequate to provide sufficient power.

The calculated number of subjects ( $n$ ) that must be enrolled in order to have 101 subjects survive to 8 years post implant with 99% probability is based on the binomial distribution. Specifically,  $n$  is such that

$$1 - \sum_{x=1}^{101} \binom{n}{x} p^x (1-p)^{n-x} > 99\%$$

where  $p$  is the probability that a subject will survive for 8 years post implant. This calculation can be performed using standard statistical software. Based on the reported 8-year survival of 60% from Aupart, et al. (2006) [8], a sample size of 195 subjects fulfills the requirements of the equation above. Based on the data collected in a previous post approval study conducted by

---

PROPRIETARY DATA: This document and the information contained herein may not be reproduced, used or disclosed without written permission from Edwards Lifesciences LLC.

Edwards (Study 98-1), a lost to follow-up rate of 7.8% was observed among subjects who reached 5 or more years of follow-up post implant. The sample size is further inflated to 225 to account for up to a 15% rate of lost to follow up.

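### The primary 8-year NYHA test counts a subject who died in Class I/II as in Class I/II at 8 years, so its result is a last known class and should not be reported as 8-year status

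*Combined protocol and SAP*

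**What the plan says.** The primary effectiveness endpoint (Section 4.2.3) is: "Proportion of subjects in NYHA Functional Classification I and II at 8 years post-implant". In the hypothesis of Section 11.1, p "is the proportion of the subjects in NYHA Class I or Class II at 8 years post implant". Neither says whether subjects must be alive.

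The planning does say so. Section 11.1 states: "The expected proportion of the alive subjects in NYHA class I or II at eight years is above 90" percent, taken from earlier-valve subjects with a valid NYHA assessment. It concludes that "the sample size of 101 subjects with NYHA data at 8 year post implant is more than adequate". On enrolment it adds: "The sample size is further inflated to 225 to account for up to a 15% rate of lost to follow up".

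Sections 11.2 and 11.4 define a wider primary set: everyone who survived the implant and has at least one NYHA class afterwards. Section 11.4 fills in the missing 8-year classes: "For subjects who die, withdraw or are lost to follow-up before reaching the 8 year follow-up visit, the last observed NYHA classes" are used. It then states that "those subjects will be counted as failures if they were in NYHA Classes III or IV at the time those events occurred". If status at the event is unknown, the last assessment before it decides.

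Section 11.6 plans each effectiveness test twice, on available cases and with the last observation carried forward, and will compare the two. The purpose it gives is to examine loss to follow-up; death is not mentioned. Section 11.4 also plans, for each annual report, the "proportion of subjects who died and were in NYHA Classes III and IV at death or at their last known NYHA classification". Section 11.3.2 gives Kaplan-Meier survival.

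Section 10.5 ends follow-up soon after an explant and keeps the data. Section 11.2 includes data up to explant. The event list in Section 11.4 does not name explant.

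**The concern.** A subject who dies at year 2 in Class II enters the primary test as a success for year 8. Carry-forward is sometimes harmless when few values are missing, but here the plan itself expects 40% of subjects to have died by 8 years. A large part of a result labelled as 8-year status would then describe people at earlier times, most of whom had died.

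The population tested is also not the one behind the expected rate of above 90%. The primary test and the available-case test answer different questions and can give different answers. The comparison that might show this is framed around loss to follow-up, the smaller source of carried-forward values. At stake is what a reader may conclude about functional status 8 years after implant.

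**Working it through.** **Plan's own figures first.** One-sided exact binomial test at 0.05 against 75% (Sections 11.1 and 11.4). The cut-off c(n) is the smallest r with P(X ≥ r | n, 0.75) ≤ 0.05.

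- n = 45: cut-off 39, alpha 0.0446, power at 90% is 84.1%. The plan states 85%, so this reproduces within rounding.
- n = 101: cut-off 84, alpha 0.0335, power 98.9%.
- Enrolment: P(X ≥ 101 | 195, 0.60) = 0.992, above the required 99%; 195 × 1.15 = 224.25, rounded up to 225.

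**How many outcomes are carried forward.** Inputs from Section 11.1: 225 implanted, 60% alive at 8 years, up to 15% lost.

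- No loss: 225 × 0.60 = 135 alive; 225 − 135 = 90 carried forward, all deaths; 90/225 = 40%.
- 15% of survivors lost: 135 × 0.85 = 114.75, about 115 assessed; 225 − 115 = 110 carried forward; 110/225 = 49%. This takes loss as independent of death.

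The total of 225 is an upper bound, because a subject who dies before the first post-implant NYHA assessment leaves the set.

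**Chance that each test passes.** Let p be the true Class I/II proportion among assessed survivors and q the share of carried-forward subjects last in Class I/II. The documents give no value for q, so it is varied. With X ~ Bin(n assessed, p) and Y ~ Bin(n carried, q) independent, the carry-forward test passes if X + Y ≥ c(225) = 180. The available-case test passes if X ≥ c(n assessed), which is 110 for n = 135 and 95 for n = 115. All results are exact.

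| Split (assessed/carried) | p | q | Carry-forward passes | Available-case passes |
|---|---|---|---|---|
| 135/90 | 0.75 | 0.90 | 69% | 4.7% |
| 135/90 | 0.75 | 0.80 | 16% | 4.7% |
| 135/90 | 0.75 | 0.75 | 4.6% | 4.7% |
| 135/90 | 0.90 | 0.75 | 96% | 99.9% |
| 135/90 | 0.90 | 0.60 | 25% | 99.9% |
| 115/110 | 0.75 | 0.90 | 85% | 3.4% |
| 115/110 | 0.90 | 0.75 | 88% | 99.5% |

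**Chance that the two tests disagree.**

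- Both groups at 90%: under 0.1% at 135/90, about 0.5% at 115/110.
- p = 0.90, q = 0.75: about 4% at 135/90, about 12% at 115/110.

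**Other assumptions, with p = 0.75 and q = 0.90.** If 10 early deaths leave the set (135/80), carry-forward passes 56% of the time. If 8-year survival were 75% (169/56), it passes 35%.

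**All-implanted view.** If survivors are at 90% and none is lost or explanted, 135 × 0.90 / 225 = 54% of implanted subjects are alive and in Class I/II. If 20 of the 135 are lost, the figure lies between 115 × 0.90 / 225 = 46% (all failures) and (115 × 0.90 + 20) / 225 = 55% (all successes).

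**The case against.** The rule is written down in advance, its consequence for failures is stated openly, and the analysis is labelled primary. It is a deliberate last-status analysis. It is not blind to decline: a subject known to be in Class III/IV at death fails even if the last visit recorded a better class. Deaths are also reported through Kaplan-Meier curves and the annual Class III/IV figures. All of this stands. It does not make a class recorded before death a status at 8 years.

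Four stronger readings are tempting, and the documents do not support them.

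- *The test is biased in favour of the valve.* The direction depends on q, which is not given. When q is low, the carry-forward test is the stricter one. The nearest figure in the plan, above 90% at each annual visit on the earlier valve, is not q, but with both groups at 90% the tests agree.
- *The sample size is wrong.* The planning figures reproduce, and power is ample on the 101 subjects planned.
- *The primary set should be replaced by assessed survivors.* That would remove explants and Class III/IV deaths from the primary test of a valve study. It is a debatable trade, not a correction.
- *No test leads, or explants are left out.* Sections 11.2 and 11.4 name a primary analysis, and Section 11.2 keeps data up to explant. What is missing is wording: explant in one list, and death in Section 11.6.

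The 69% and 25% pass rates are also conditional. The first needs survivors exactly at the null value, the second a q well below the survivors' rate.

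**Conclusion.** The concern holds as a mismatch between what the primary test measures and what its result is called. On 60% survival and up to 15% loss, 40% to 49% of its outcomes are not 8-year classes, and about 90 of them come from deaths. If observed survival or retention is better, the share falls: at 75% survival and no loss it is 56/225, or 25%.

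Whether the conclusion changes depends on q. It hardly matters if both groups are near 90%. It matters if survivors do worse than planned, or if q falls well below their rate. Even when both tests pass, a reported 90% would stand for 54% of implanted subjects alive and in Class I/II. This should be corrected before the 8-year analysis, but it does not invalidate the design.

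**What to change.** Keep the primary analysis set and change the text around it.

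1. Section 11.4: describe the carry-forward result as *last known NYHA class through 8 years*, not as status at 8 years.
2. Sections 11.4 and 11.6: base any statement about NYHA class at 8 years on the available-case test already planned, worded as conditional on being alive and assessed at 8 years. Report both tests side by side, and let the comparison cover death as well as loss to follow-up.
3. Report beside them, without a test, the proportion of all implanted subjects who are alive, unexplanted and in Class I/II at 8 years. Count losses and withdrawals first all as failures, then all as successes. Add the numbers of deaths, explants, withdrawals and losses by last NYHA class.
4. Section 11.4: add explant to the list of events, consistent with Sections 10.5 and 11.2.

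The cost is a little more analysis, a less favourable figure beside the headline, and an amendment under Section 17.3 (FDA agreement, then IRB/EC approval). No new visits or data are needed. The available-case statement assumes that lost survivors resemble those seen, which is why item 3 asks for both bounds.

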### **Hemodynamic Performance**

Echocardiography data will be obtained preoperatively, early postoperatively and/or discharge, at 6-months and at 1, 5 and 8 year follow-ups. Descriptive statistics for the continuous echo variables and change from baseline (e.g. mean, standard deviation, and range) will be categorized by time interval and size. Regurgitation data will be summarized using frequency at each severity level.

Improvement in regurgitation at one year will be analyzed via the Jonckheere-Terpstra [11] test. Change at one year from baseline for all other hemodynamic outcomes will be analyzed using paired *t*-tests.

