## 5. STUDY DESIGN

This is a prospective, single-arm, multi-center study to be conducted in the US and outside the US (OUS). A minimum of 225 subjects will be implanted (Section 11.1 Sample Size) to obtain long term data from 101 subjects at 8 years post implant of the Carpentier-Edwards PERIMOUNT

Magna Ease Pericardial Aortic Bioprosthesis, Model 3300TFX (Magna Ease valve). Subject enrollment will not start in the US before obtaining FDA approval of this post approval study.

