## 7. STUDY MATERIALS

### 7.1. DEVICE DESCRIPTION

The Carpentier-Edwards PERIMOUNT Magna Ease Pericardial Bioprosthesis Model 3300TFX is a trileaflet bioprosthesis comprised of bovine pericardium that has been preserved in a buffered glutaraldehyde solution and mounted on a flexible frame. The bioprosthesis is treated according to the Edwards ThermaFix® process, which involves heat treatment of the tissue in glutaraldehyde and uses ethanol and polysorbate 80. The frame is designed to be compliant at the orifice and commissures. The lightweight frame is made of cobalt-chromium alloy, a corrosion-resistant alloy chosen because of its superior spring efficiency and fatigue-resistant characteristics, and is covered with a woven polyester fabric [REDACTED].

A thin cobalt-chromium alloy /polyester film laminate surrounds the base of the wireform frame providing structural support for the orifice. A silicone rubber suture ring is attached to the cobalt-chromium alloy frame that is covered with a porous, polytetrafluoroethylene cloth to facilitate tissue ingrowth and encapsulation. The aortic sewing ring has been scalloped to conform to the natural aortic annulus. The compliant nature of the suture ring also facilitates coaptation between the bioprosthesis and an often irregular calcified tissue bed.

The original aortic Carpentier-Edwards PERIMOUNT Pericardial Bioprosthesis, Model 2700, has been commercially available in the US since 1981 and the Model 2900 has been commercially available on the international market since 1983, Model 2800 (RSR) has been commercially available in the US since 1996 and Model PERIMOUNT Magna 3000TFX has been CE marked since 2004 and was launched in the US in 2005. The aortic Carpentier-Edwards PERIMOUNT Magna Ease obtained CE marking in December 2006.

The modifications resulting in Carpentier-Edwards PERIMOUNT Magna Ease Pericardial Bioprosthesis, Model 3300TFX is based on the continuing clinical experience in pericardial valves. The profile height on the Magna Ease bioprosthesis has been reduced to facilitate implantation in patients with small aortic roots.

The Model 3300TFX Magna Ease valve is available in the following sizes: 19 mm, 21 mm, 23 mm, 25 mm, 27 mm and 29 mm.

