## 8.1 PREOPERATIVE PROCEDURES

The investigator will determine and record each subject's demographics (date of birth, sex), physical assessment (heart rate, height, weight and blood pressure), New York Heart Association (NYHA) functional class, cardiac rhythm, cardiovascular medical history/risk factors, non-cardiovascular conditions, previous cardiovascular procedures/interventions, anti-thromboembolic medications and coagulation profile.

Blood data is required for each subject preoperatively and should be collected within 30 days prior to valve replacement. The following parameters will be collected: white blood cell count (WBC), red blood cell count (RBC), hemoglobin, hematocrit, reticulocytes, platelet count, haptoglobin and serum lactic dehydrogenase (SLDH). Should the serum LDH be elevated, it should be fractionated. Preoperative data is indicated on the CRF and is outlined in Table 2. The investigator or designee will also indicate if the parameters are within normal ranges or not and whether the change is clinically significant. A QOL survey (EQ-5D) will be completed by the subject pre operatively.

In addition, pre-operative echocardiographic evaluation is optional for this study; however if performed, the investigator should document the findings. The echocardiography information will be indicated on the CRF.

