## 11.6 MISSING DATA

All statistical tests on the effectiveness endpoints will be performed in two ways: (1) using only those subjects with available required for endpoint analysis and (2) by using the method of last observation carried forward (LOCF). Both methods of analyses will then be compared. However, both methods will be used for the comparison of NYHA classification at 8 year post implant to OPC (75%) and for the comparison of hemodynamic performance one year to baseline for the purpose of investigating the effect of loss-to-follow-up.

NYHA classification and hemodynamic performance will be summarized at each of the follow-up interval. In addition, the NYHA classification will only be statistically compared to OPC at 8 years post implant and only the one year post implant hemodynamic performance will be statistically compared to baseline.

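### One-year improvement in regurgitation is a within-subject comparison, but it is assigned Jonckheere-Terpstra, an independent-groups test; a paired ordinal test should be named

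*Combined protocol and SAP*

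**What the plan says.** Section 11.4 (Hemodynamic Performance) says: "Improvement in regurgitation at one year will be analyzed via the Jonckheere-Terpstra [11] test". It gives no ordered groups, response variable, direction or blocking by subject. The next sentence handles everything else by a within-subject method: "Change at one year from baseline for all other hemodynamic outcomes will be analyzed using paired" t-tests. Section 11.6 fixes the contrast: "only the one year post implant hemodynamic performance will be statistically compared to baseline". It asks for each effectiveness test to be run twice, once "using only those subjects with available required for endpoint analysis" and once with the last observation carried forward (LOCF). Section 5 describes a single-arm study, so there is no treatment factor to order.

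Two other details bear on the point. Section 11.4 says that descriptive statistics "will be categorized by time interval and size", but that sentence is about the continuous echo variables; regurgitation has its own sentence, by severity level. Section 8.1 says that "pre-operative echocardiographic evaluation is optional for this study", while Section 8.3.1 requires an early postoperative or discharge echo. Section 11.4 does not say which of the two is the baseline. Section 11.1 sets a 0.05 level without saying whether this test is one- or two-sided.

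**The concern.** Jonckheere-Terpstra takes its null variance from independent observations. Here each subject supplies a baseline grade and a one-year grade, and improvement means change within the subject. Regurgitation is the only hemodynamic outcome not given a paired test, and nothing in the plan explains the exception.

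Two things are at stake. If the groups are the two time points, the p-value is miscalibrated whenever a subject's two grades correlate, and power is lost when that correlation is positive. If some other grouping was meant, the test may answer a different question. Because the groups are not named, two analysts could run different tests and both claim to follow the plan.

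**Working it through.** The plan gives no power, effect size or sample size for this test, so there is no figure of its own to reproduce. The check covers what the test does under each possible grouping, and how large the effect could be.

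**Step 1: two time points as groups.** With two groups, tie-corrected Jonckheere-Terpstra is the rank-sum (Mann-Whitney) test. On a trial data set both gave p = 0.3923. It uses the variance for two independent samples. If a subject's two grades have correlation r, the true standard deviation of the Z statistic is about √(1 − r), so a nominal one-sided 0.05 test has actual size of about Φ(−1.645/√(1 − r)):

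- r = 0.45: 1.645/0.742 = 2.22, size about 0.013
- r = 0.27: 1.645/0.854 = 1.93, size about 0.027
- r = 0.08: 1.645/0.959 = 1.72, size about 0.043
- r = 0: size 0.050
- r = −0.25: 1.645/1.118 = 1.47, size about 0.071

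**Step 2: simulation.** All inputs here are assumptions, because the documents give no grade distribution, correlation or number of pairs.

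- Five grades (0 to 4) with baseline shares .35/.30/.20/.10/.05, mean grade .30 + .40 + .30 + .20 = 1.20.
- Small improvement .42/.30/.17/.08/.03, mean .30 + .34 + .24 + .12 = 1.00. Moderate .50/.30/.14/.05/.01, mean 0.77. Large .65/.27/.06/.015/.005, mean 0.455.
- A latent bivariate normal. Latent correlations 0.5, 0.3, 0.1 and −0.3 give grade correlations of about 0.45, 0.27, 0.08 and −0.25.
- 150 complete pairs out of the minimum of 225 implanted; one-sided 0.05; 100,000 data sets per null setting and 40,000 per power setting.

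| Latent correlation | Type I error, rank-sum | Small-shift power, rank-sum v signed-rank |
|---|---|---|
| 0.5 | 0.015 | 0.42 v 0.65 |
| 0.3 | 0.029 | 0.43 v 0.55 |
| 0.1 | 0.042 | 0.44 v 0.47 |
| 0 | 0.050 | 0.45 v 0.45 |
| −0.3 | 0.071 | not computed |

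The signed-rank test held 0.049 to 0.051 throughout. The simulated sizes agree with step 1. For the moderate shift, power is 0.99 v 1.00 at correlation 0.5 and 0.95 v 0.97 at 0. For the large shift it is 1.00 v 1.00.

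A second simulation used other assumed shares (.35/.25/.20/.12/.08), 100 pairs and a two-sided 0.05 level, with 2,000 data sets per setting. Rank-sum type I error was 0.007 at latent correlation 0.5, 0.025 at 0.3 and 0.054 at 0. Power for a 0.2 SD improvement, rank-sum v signed-rank, was 0.19 v 0.40, 0.21 v 0.32 and 0.26 v 0.26. The pattern is the same.

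**Step 3: other groupings.**

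- *Ordered visits (preoperative, discharge, 6 months, one year).* The same subjects appear in every group, so pairing is again ignored. This was not simulated.
- *Baseline grade as the group, one-year grade as the response.* This tests association. With 150 subjects it rejected in 94% of data sets with no improvement at latent correlation 0.3, and in about 5% with a large improvement at correlation 0.
- *Valve size as the group (Section 7.1: "available in the following sizes: 19 mm, 21 mm, 23 mm, 25 mm, 27 mm and 29 mm"), change in grade as the response.* This is a valid test, but of a trend across sizes. With assumed size shares it rejected in about 5% of data sets when a large improvement was equal across sizes.

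**Step 4: missing baseline echoes.** Suppose half the baseline echoes are missing at random. The unpaired test then uses 75 baseline and 150 one-year grades, and the signed-rank test uses 75 pairs. Small-shift power, unpaired v paired, is 0.31 v 0.41 at latent correlation 0.5, 0.32 v 0.34 at 0.3, 0.34 v 0.30 at 0.1 and 0.34 v 0.28 at 0.

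**The case against.** The strongest reply is that the practical error may be small. If baseline is the preoperative echo, that grade comes from the valve being replaced, and its correlation with the grade of the new valve may be low. At latent correlation 0 to 0.1 the rank-sum test is almost correctly sized and loses little power, and for a large improvement the choice of test makes no difference. If many optional preoperative echoes are missing, the paired test can even be slightly weaker. All of this stands. It limits the size of the point, but it does not make an independent-groups test the right one for a within-subject contrast.

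It is also fair to say that grouping by baseline grade or by valve size is unlikely to be what was meant. The first sits badly with the word improvement, and the by-size sentence in Section 11.4 covers continuous variables only. Those groupings show that other choices of groups do not rescue the test; they are not evidence of what the sponsor would run.

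The baseline gap is narrower than it may look. Section 11.5 ties baseline risk to preoperative variables, and Section 11.4 lists the preoperative echo first, so usage leans that way. What remains is a clarification. The one-year test is also secondary, with no stated success criterion.

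**Conclusion.** The point holds in limited form. As written, the test does not match the comparison that the plan describes. On the natural reading it is an unpaired rank-sum test. Under the assumed grades and 150 pairs, its one-sided type I error runs from about 0.015 at latent correlation 0.5 to 0.05 at zero, and small-shift power is 0.42 v 0.65 at 0.5 and equal at zero. These sizes rest on assumed grades, correlations and number of pairs; the size and direction of the error in this trial are unknown.

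A reader might infer more than the documents support:

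- *That the test inflates false positives.* That needs a negative correlation between a subject's two grades, and nothing in the documents suggests one. With positive correlation the error is conservative.
- *That a paired test is always more powerful.* Step 4 shows that it is not when many baselines are missing and correlation is near zero.
- *That the main conclusions are at risk.* The primary safety tests, the NYHA test and the sample size do not depend on this analysis. The choice of test affects only the one-year regurgitation result. The baseline clarification reaches further, to the paired t-tests and every change-from-baseline summary, including year 8.

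**What to change.** In Section 11.4, replace Jonckheere-Terpstra with one named primary method: the Wilcoxon signed-rank test on within-subject change in regurgitation grade, among subjects with both a baseline and a one-year grade. State whether it is one- or two-sided. Report the number of complete pairs, and keep the LOCF rerun that Section 11.6 requires. Add a marginal homogeneity test as a sensitivity analysis. Signed-rank ranks the differences between grades and drops unchanged subjects; at zero correlation under the assumed null shares these are .35² + .30² + .20² + .10² + .05² = 0.265 of pairs. If a trend across valve sizes is of interest, list it as a separate analysis with its groups and response named.

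As a secondary clarification, state which echo is the baseline, preoperative or early postoperative/discharge, and use the same one for the paired t-tests and all change-from-baseline summaries.

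The cost is a few sentences and one count in a table, with no new data or procedures. The change must still go through Section 17.3: a written amendment agreed by FDA, then IRB/EC approval. Subjects without a baseline echo drop out of the test, as they already do from the paired t-tests. With half missing and zero correlation, that means power of about 0.28 instead of 0.34 for a small shift.
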